
Exclusion Criteria:
	
 • Suspected or known to be sensitive or allergic to midge bites; • Participated in an interventional study (other than a biting insect challenge study) in the previous 3 months; • Participated in a biting insect challenge study in the previous 72 hours; • Aware of having any cardiovascular or respiratory disorder (whether active or inactive) (e.g. asthma); • Individuals with localized skin disorders affecting the forearm; • Allergic to any of the test product ingredients; • Extensive tattooing or other conditions of the forearm which would make interpretation of the bite test results difficult; • Women who are pregnant, nursing or intending to become pregnant; • Previous anaphylaxis; • Aware of having a compromised immune system;(an immune system that is temporarily or permanently incapable of working at full capacity); • Phobia of flying insects; • Travelled to a mosquito-borne disease endemic area in the last 3 months.

Efficacy Endpoint(s):
	
Primary: Median Complete Protection Time for the repellent products, tested against Culicoides nubeculosus midges.
 
Secondary: Percentage protective efficacy of the repellent products, tested against Culicoides nubeculosus midges.

Safety Endpoint(s):
	
Adverse event data will be collected and summarised.

Statistical Methods:
	
Median Complete Protection Time will be calculated using the Kaplan Meier survival-function.
 
Two-way analysis of variance followed by Tukey's tests or general linear mode will be used to compare the mean complete-protection time for the tested repellents

Investigation Site(s):
	
Single-centre: Arthropod Control Product Test Centre (arctec), Chariot Innovations Limited, a wholly-owned subsidiary of the London School of Hygiene & Tropical Medicine (LSHTM).

TABLE OF CONTENTS

1. INTRODUCTION.....	7
2. OBJECTIVES.....	7
3. STUDY DESIGN	7
3.1. STUDY ENDPOINTS.....	8
3.2. RISKS AND BENEFITS	8
3.2.1. Midges	8
3.2.2. Product	8
4. PARTICIPANT ENTRY	9
4.1. SCREENING PROCEDURES	9
4.2. INCLUSION CRITERIA	9
4.3. EXCLUSION CRITERIA	10
4.4. WITHDRAWAL CRITERIA.....	10
5. RANDOMISATION AND ENROLMENT	11
6. TREATMENTS	11
7. SAFETY REPORTING FOR NON-DRUG TRIALS.....	12
7.1. DEFINITIONS	12
7.2. REPORTING PROCEDURES	12
7.2.1. Non serious AEs	12
7.2.2. Serious AEs	12
8. TEST METHODOLOGY.....	13

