APPENDIX 3: FLOWCHART FOR SAFETY REPORTING24

APPENDIX 4: SAMPLE SIZE CALCULATION FOR A COMPARISON TRIAL BETWEEN A POSITIVE CONTROL AND TWO MIDGE REPELLENT PRODUCTS.....25

1. Introduction

Mosquitoes, midges and other biting insects are vectors of extremely important diseases such as malaria, yellow fever, filariasis and many viruses and also may be of great nuisance value. The use of repellent products can provide added personal protection from disease transmission and nuisance bites. New effective repellents would offer an additional option for protection against biting insects. The tests carried out by *arctec* provide important information on the effectiveness of skin repellents, which will be used for label claims to accurately inform consumers and registration purposes.

The aim of this study is to determine the effectiveness of two topically applied insect repellent products provided by NEO-INNOVA HEALTHCARE LIMITED and one positive control containing the UK repellent brand 'Smidge'.

2. Objectives

Primary objective: To determine and compare the median complete protection time (CPT) of two insect repellent products and a positive control against *Culicoides nubeculosus* (midges).

Secondary objective: To determine and compare the protective efficacy of two insect repellent products and a positive control against *Culicoides nubeculosus* (midges).

3. Study Design

This is a single-centre, single-arm study with all participants testing two formulations containing PMD and a positive control product containing Picaridin. The control for each test is an untreated arm. There is no blinding or randomisation employed, since the outcome measures are based on midge behaviour. Repellent product testing takes place in a laboratory setting using 7 participants (preferably gender balanced). Each participant will test both PMD formulations and a positive control product (see section 8).

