4.4. Withdrawal Criteria

Participants can stop at any time without giving a reason for withdrawing. Data collected to the point of withdrawal will be used in the analysis of the study, unless the participant requests that their data is not used, in which case it will be removed from the database. Participants may also be removed at the discretion of the Chief Investigator, where continued participation may affect the safety of the participant or where there is a development of any condition which might interfere with study participation.

5. Randomisation and Enrolment

Volunteers will be recruited through standard recruitment methods, including emails, posters, leaflets and other advertising routes to staff and students of LSHTM and other members of the public. Volunteers will be fully informed before the study and it will be made clear that they can withdraw from the study at any time. Volunteers will be given and asked to read the Participant Information Sheet and Product Information Sheet which describes the tests which they will take part in, and a consent form which must be signed before the test begins.

6. Treatments

NEO-INNOVA HEALTHCARE LIMITED will provide two products to be tested containing 35% and 40% PMD, and one positive control containing 20% Picaridin. The positive control product is currently marketed as a midge repellent, while PMD is a recommended active ingredient, which has been evaluated for safe use by the U.S. Environmental Protection Agency (USEPA)¹. Therefore, humans have already used the products. The products will be applied at a rate of 1.67 $\mu\text{l}/\text{cm}^2$. The products will be applied to the measured forearm of each participant. This dose does not exceed the maximum daily limit for PMD or Picaridin.

7. Safety Reporting for Non-Drug Trials

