8.4. Protective Efficacy

In order to determine Protective Efficacy over time, the tests will continue every hour as described in section 8.3 until at least 50% of midges are probing or biting compared with control (i.e. 50% Protective Efficacy), or until 12 hours post application.

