9.2. Data analysis

The endpoint for Complete Protection Time will be time to treatment failure for each participant test. Treatment failure is the time at which the product no longer provides complete protection, which is determined as the time at which one probe or bite occurs in a 1 minute test, followed by a confirmatory probe or bite within 30 minutes. Using IBM SPSS Statistics 20, the times to treatment failure will be analysed using Kaplan-Meier Survival functions, and from these the median Complete Protection time and 95% confidence intervals will be calculated.

A linear regression will be used to compare the mean complete-protection time for the tested repellents. As a sensitivity analysis we will use linear regression to estimate the mean CPT difference between groups, but we will generate robust standard errors by relaxing the assumption of independence of observations between the same participant within the study, allowing for correlation between observations from the same participant in the variance-covariance matrix.

The Protective Efficacy over time from application will be calculated using the formula below at each hour and presented as a summary table and graph. Using IBM SPSS Statistics 20, the PE will be analysed using a two-way analysis of variance followed by Tukey's tests or generalised linear model.

$$PE = \frac{\text{Midges probing on control} - \text{Midges probing on treatment}}{\text{Midges probing on control}} \times 100$$

Adverse Events will be tabulated and included in the study report. Adverse events occurring after the end of participant participation but before the end of the study will be listed separately.

10. Safety and Data Monitoring

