10.2. Adverse events

Volunteers will be monitored throughout the duration of the tests by investigational staff for any adverse events. If any adverse events related to insect bites or the repellent products are apparent at any time during the trial, testing will stop immediately and details of how to access treatment will be offered. Volunteers can only participate in a test a minimum of 72 hours after the screening bite test and participants with known allergies to any of the product ingredients will not be eligible to take part.

Within 72 hours after laboratory testing an email will be sent to participants asking them to report any adverse events that might have occurred since the end of testing.

Adverse events that occur >72 hours after the end of participation in the trial will be passively monitored.

An adverse event which is ongoing at the time of participant withdrawal or completion will be followed up until it resolves or until 30 days after the participant terminates from the study, whichever comes first.

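### The primary objective is to compare median CPT, but the only planned comparison is of mean CPT, under two different models, with the main regression treating each participant's three tests as independent and no rule for unfinished tests

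*Combined protocol and SAP*

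**What the plan says.** - **Objective and endpoint.** The synopsis and Section 2 set the primary aim: "To determine and compare the median complete protection time (CPT) of two insect repellent products and a positive control". Section 3.1 and the synopsis both give median CPT as the primary endpoint.
- **Description.** In Section 9.2, "the times to treatment failure will be analysed using Kaplan-Meier Survival functions", giving a median and 95% confidence interval. No log-rank test, survival model or test of medians is named.
- **Comparison in Section 9.2.** "A linear regression will be used to compare the mean complete-protection time for the tested repellents". A sensitivity version keeps the regression and replaces its standard errors with ones that allow correlation within participant.
- **Comparison in the synopsis.** Two-way ANOVA with Tukey's tests "or general linear mode will be used to compare the mean complete-protection time for the tested repellents". The factors are not named.
- **Design.** Section 3 has "all participants testing two formulations containing PMD and a positive control product containing Picaridin".
- **End of a test.** Section 8.4 continues testing to 50% protective efficacy "or until 12 hours post application". If a related adverse event appears, Section 10.2 says "testing will stop immediately and details of how to access treatment will be offered". For withdrawals, Section 4.4 says "Data collected to the point of withdrawal will be used in the analysis of the study". None of these says what CPT an unfinished test contributes to the comparison of means.

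**The concern.** Three things are left open on the primary endpoint.

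1. The objective asks for a comparison of medians, and no planned method makes one. The two places that describe the CPT comparison name different models.
2. The main regression in Section 9.2 ignores that each participant contributes three results. The sensitivity analysis works by relaxing independence, which shows that the main one assumes it.
3. A regression or ANOVA of raw times needs a number for every test. A test still protected at 12 h, or stopped early, has no observed failure time.

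If the text stays as it is, the model and the value given to unfinished tests could be chosen after the data are seen, in an unblinded study whose results inform labelling (Section 3.2.2). Power that the design already provides would also be given up.

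**Working it through.** **1. Reproduce the plan's sample size.** Appendix 4 uses n = (2σ²/δ²)·f, with f = (z₁₋α/₂ + z₁₋β)². The SD is not stated. Solving for σ across all 30 cells of the two tables, with n rounded up, gives 68.81 to 68.98 min; 68.9 is used here and reproduces all 30. With α = 0.05/2 = 0.025 two-sided and 80% power, f = 9.505. So n = 2 × 68.9² / 120² × 9.505 = 6.27, rounded up to 7, as stated.

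**2. Effect of ignoring participant.** If ρ is the correlation between two results of one participant, the true standard error of a product difference is σ√(2(1−ρ)/7). The independence regression estimates about σ√(2/7) = 36.8 min whatever ρ is. The true value is 36.8, 30.8 and 26.0 min at ρ = 0, 0.3 and 0.5, so the regression's standard error is too large when ρ > 0.

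Simulation: 200,000 trials, 7 participants × 3 products, normal CPT, SD 68.9, times capped at 720 min. Means are 480/480/480 (null) or 480/600/480, with two-sided alpha 0.025. ρ is not in the documents, so a range is shown.

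| ρ | Independence regression (18 df): false positives | Power | Product + participant (12 df): false positives | Power |
|---|---|---|---|---|
| 0 | 2.5% | 0.78 | about 2.5% | 0.75 |
| 0.3 | 1.0% | 0.82 | about 2.5% | 0.89 |
| 0.5 | 0.4% | 0.84 | about 2.5% | 0.97 |

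**3. The robust sensitivity regression.** It leaves the estimate unchanged and has only 7 clusters. In the same simulation, uncorrected clustered errors with a normal reference give about 8% false positives at nominal 2.5%. With the factor (7/6)(20/18) and t on 6 df the rate is about 2%, with power about 0.59, 0.75 and 0.89 at ρ = 0, 0.3 and 0.5. Section 9.2 does not say which would be used.

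**4. Tests still protected at 12 h.** If such tests count as 720 min, the mean is E[min(X,720)] = μΦ(z) − σφ(z) + 720(1 − Φ(z)), with z = (720 − μ)/σ. The documents give no expected CPT, so a range is shown for a true difference of 120 min.

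| Means compared (min) | Longer-acting product's tests reaching 12 h | Difference in capped means (min) |
|---|---|---|
| 480 vs 600 | 4% | 598.9 − 480.0 = 119 |
| 540 vs 660 | 19% | 652.7 − 539.9 = 113 |
| 600 vs 720 | 50% | 692.5 − 598.9 = 94 |
| 660 vs 780 | 81% | 712.7 − 652.7 = 60 |

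The capped difference is a valid quantity, mean protected time up to 12 h, but the plan does not declare it.

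**5. Tests stopped early.** If one of a product's 7 tests stopped at time s and s were entered as its CPT, the product mean would fall by (E[min(X,720)] − E[min(X,s)])/7. For a product averaging 600 min this is 68, 51 or 34 min for a stop at 2, 4 or 6 h. For one averaging 240 min it is 17 min for a stop at 2 h and 4 min for a stop at 4 h. Stop rates and times are not in the documents, so these figures show only how strongly the effect depends on the assumptions.

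**The case against.** - **The synopsis may already hold the right model.** CPT gives one value per participant per product, so participant is the natural second factor of a two-way ANOVA. This stands in part. The factors are not named, and Section 9.2 names a different model.
- **The independence regression does little harm.** Its power of 0.78 to 0.84 is near the planned 0.80, and its false-positive rate does not exceed nominal. This stands: a reader might infer that ignoring the pairing inflates false positives, but it does the opposite. The loss is relative to a better model at no cost in participants.
- **Mean and median differences may coincide.** They do for distributions of the same shape shifted in time, and every figure above assumes normal CPT. The mismatch is therefore not quantified here. Appendix 4 is sized on means, so a drafting slip is a fair reading. The plan does not state the shape assumption, and the 12 h cap breaks it.
- **Large bias from unfinished tests is tempting to infer.** The documents do not support it. They give no expected CPT and no stop rate, and screening removes strong bite reactors (Section 4.1), which should reduce bite-related stops. Scoring a stop as a failure would contradict Section 9.2, which defines failure by a confirmed probe or bite. Kaplan-Meier can hold such tests by censoring, so the gap mainly affects the comparison of means.

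**Conclusion.** The point holds as a gap in specification with a measurable cost in power. The objective and endpoint are medians, the only comparison is of means, and Section 9.2 and the synopsis give different models for it. The main regression in Section 9.2 wastes the within-participant design: at correlation 0.3 and 0.5, power is about 0.82 and 0.84 where 0.89 and 0.97 are available. These figures rest on normal CPT, the back-solved SD of 68.9 min, Appendix 4's 120 min difference and alpha of 0.025, and an assumed correlation.

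The missing rule for 12 h and early-stopped tests is real, but its effect has no derivable size. It could be almost nil. A reader might also conclude that 7 participants is the wrong number; nothing here shows that, since the stated figure reproduces. The plan should be corrected before the data are analysed.

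**What to change.** In Section 9.2 and the synopsis:

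- Name one main CPT comparison: a model with product and participant as factors, replacing the independence regression. This is the two-way ANOVA form that the synopsis already names.
- State that tests still protected at 12 h count as 720 min, so that the quantity compared is mean protected time up to 12 h.
- State that tests stopped earlier without a confirmed probe or bite are not failures and are right-censored. The method is the statistician's choice; restricted-mean pseudo-values are one option. Add a sensitivity analysis, because stops under Section 10.2 may be related to the product or the bites.
- Keep the Kaplan-Meier medians with 95% confidence intervals as the description of each product.
- If the robust regression stays as a sensitivity analysis, state its small-sample correction and reference distribution.

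Align the objective wording (synopsis, Section 2) and the endpoint wording (synopsis, Section 3.1) with the chosen comparison.

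The cost is text and minor programming, with no extra participants or procedures. Two downsides remain. The participant factor loses about 3 to 4 points of power if within-participant correlation is zero. The restricted mean says nothing about protection beyond 12 h.

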8.1. Midge Fitness Check and control test (combined)

Before the start of each test, the participant will insert a bare (control) left arm into the cage for 1 minute to assess biting activity of the midges. Only cages with at least 10 midges landing within one minute will be used in the tests. This same procedure is used to assess whether volunteers are attractive to the midges. The number of midges probing or biting the arm after 1 minute will be counted and recorded (to provide biting rate data of the control test for the Protective Efficacy endpoint) and the arm removed from the cage.

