10.3. Data Monitoring

With the exception of the Volunteer Questionnaire, which is completed by the participant, all data collected will be recorded in the case report forms (CRF) and signed by the person completing the CRF. The CRF is considered to be source data.

Data to be collected are: Participant number and date of visit on every page, confirmation of informed consent, date of birth, eligibility details, bite test details (midge species, timing, 10 min and 72 h assessments), test visits (eligibility checklist, forearm measurement, product details, product application details, arm-in-cage testing data (time, fitness check, No. midges probing control arm, No. midges probing treated arm)) and adverse event monitoring.

Raw data from the CRF are then entered into an Excel spreadsheet for analysis and saved on the shared "i" drive (with access limited to members of the study team). Data will be double entered and verified to ensure accuracy. CRFs will be kept in locked storage.

Information in the database for each test will be linked to a relevant SOP, risk assessment, contract, and files of statistical analysis and location of report copy.

11. Regulatory Issues

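### The comparison of complete protection time leaves out the time-0 untreated-arm count recorded in every session, so unequal biting pressure between cages can bias the product difference

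*Combined protocol and SAP*

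**What the plan says.** Section 9.2 gives the CPT comparison as follows: "A linear regression will be used to compare the mean complete-protection time for the tested repellents". Its sensitivity analysis is the same regression with robust standard errors, "allowing for correlation between observations from the same participant in the variance-covariance matrix". The synopsis (Statistical Methods) names a different approach, two-way analysis of variance with Tukey's tests, or "general linear mode will be used to compare the mean complete-protection time for the tested repellents". None of these includes a measure of biting pressure.

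Such a measure exists. Section 8.1 says: "Before the start of each test, the participant will insert a bare (control) left arm into the cage for 1 minute". It continues: "The number of midges probing or biting the arm after 1 minute will be counted and recorded". The stated purpose is "to provide biting rate data of the control test for the Protective Efficacy endpoint", and section 10.3 lists "No. midges probing control arm" among the case report form items.

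The cage acceptance rule in section 8.1 is a floor: "Only cages with at least 10 midges landing within one minute will be used in the tests". Section 8 puts 50 midges in a cage. Section 8.3 repeats the floor at each hourly control test and refreshes a cage that falls below it. Under section 3.2.1 a cage serves one volunteer and its midges are destroyed after the test, with at least 72 hours between product tests. Section 3 says that no randomisation is used.

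**The concern.** CPT ends at the first one or two probes or bites on the treated arm, so it depends on how many midges are trying to bite as well as on the product. Within a participant, cage, day and product change together. A participant term would remove stable differences in attractiveness to midges, but not differences between one person's own sessions.

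Chance differences in pressure only add noise. With no randomised order, however, a drift by day or midge batch can coincide with product, and then it is bias. Robust standard errors do not move a biased estimate. Protective Efficacy is scaled by the control count; the primary comparison has no such correction. Section 3.2.2 says that the results will inform product labelling.

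**Working it through.** **1. The plan's own figure.** Appendix 4 gives n = 2σ²(z₁₋α/₂ + z₁₋β)²/δ² and 7 participants for δ = 120 min, 80% power and Bonferroni α = 0.025. It does not state σ. Solving back, σ = 68.9 min with rounding up matches all 15 cells of each table. With σ rounded to 69: 2 × 69² / 120² × (2.241 + 0.842)² = 0.661 × 9.505 = 6.29, rounded up to 7. The figure reproduces.

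**2. Dependence of CPT on pressure.** Suppose a product still blocks 95% of bites. The chance of at least one bite in a 1-minute test with k biting midges is 1 − 0.95^k: 40% for k = 10, 64% for k = 20 and 87% for k = 40.

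An illustrative model of the section 8.3 procedure assumes Poisson probes and logistic loss of repellency (midpoint 6 to 10 h, scale 0.7 to 1.5 h), with hourly tests and the half-hour confirmation. Raising pressure from 10 to 20 per minute shortens mean CPT by about 32 to 64 min. Raising it from 10 to 50 shortens it by about 71 to 148 min.

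**3. Bias from imbalance.** If the count has correlation ρ with CPT and one product's mean count is shifted by m SD, the unadjusted difference is biased by ρ × 69 × m.

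| ρ (assumed) | m = 0.5 | m = 1 |
|---|---|---|
| 0.3 | 10 min | 21 min |
| 0.5 | 17 min | 35 min |
| 0.7 | 24 min | 48 min |

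In that linear setting, adjustment removes almost all the bias because the covariate is taken as error-free. A 1-minute count is not. With Poisson noise in the count and the procedure of step 2, a 1-SD imbalance gives:
- unadjusted bias of about 9 to 43 min (9/120 = 7.5% to 43/120 = 36% of the design difference);
- adjusted bias of about 4 to 9 min.

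The ranges reflect how widely pressure is assumed to vary and how fast repellency is assumed to fade. A check simulation with median pressure 20 per minute, SD of log pressure 0.2 to 0.5, midpoint 8 h and scale 0.7 to 1.5 h came within about 2 min of them.

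**4. Power.** There are 7 × 3 = 21 sessions. Residual df are 21 − 3 = 18 for product alone, 17 with the count, 12 with a participant term instead, and 11 with both. At σ = 69, δ = 120 and α = 0.025, noncentral t gives 78.3% for product alone. The lost df alone would cost 0.4 points (77.9%), but chance imbalance in the count also inflates the variance. A simulation that includes this (6,000 runs per setting, no between-participant variance) gives:

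| ρ (assumed) | Product only | + count | + participant + count |
|---|---|---|---|
| 0 | 79% | 76% | 70% |
| 0.3 | 79% | 80% | 75% |
| 0.5 | 78% | 87% | 82% |

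The count alone therefore costs about 3 points at ρ = 0 and breaks even at roughly 0.25 to 0.3. Adding a participant term as well costs about 8 points at ρ = 0.

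**The case against.** The case against acting has several parts.

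- **Pressure is already partly controlled.** Section 8 calls for host-seeking females of uniform age, 50 per cage and fixed room conditions, and section 8.3 repeats the floor hourly. This stands in part: several-fold variation between accepted cages is possible but not shown. A floor still does not equalise pressure.
- **The correlation and the imbalance are assumed.** This stands. Nothing in the documents puts the correlation above break-even, so a gain in power cannot be promised.
- **One count at time 0 is a weak proxy.** Failure may come hours later, possibly in a refreshed cage. This also stands. At ρ = 0.5 and a 1-SD imbalance, assumed covariate reliability of 0.7 or 0.5 leaves about 10 or 18 min of bias, compared with about 35 min unadjusted. Adjustment reduces the bias but does not remove it.
- **The count has practical defects.** The floor concerns landings but the count is of probing or biting, so an accepted cage could record zero and a plain logarithm would fail. Section 8.3 also lists product application before the control test, so the count may follow application. Both can be handled in the wording of the analysis.
- **The direct remedy is balanced order.** True, and adjustment is no substitute. One count cannot remove other day or order effects.

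A reader might also infer that the change costs a single degree of freedom from a model that already includes participant. Section 9.2 names no participant term, so a model with participant and count goes from 18 df to 11. Whether to include participant is a separate choice.

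**Conclusion.** The omission is real and worth correcting. A measure of biting pressure taken before the treated arm enters the cage is already on the case report form, and the primary comparison does not use it in a design where pressure can line up with product. The main gain is less bias: from about 9 to 43 min down to about 4 to 9 min for a 1-SD imbalance. These figures rest on the assumed spread of pressure, Poisson counts and the assumed loss of repellency.

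Three stronger readings are not supported. The documents do not show that such an imbalance will occur, only that nothing prevents it. They do not support a claim that adjustment removes the bias almost completely, because the count is noisy and cages may be refreshed. Nor do they support a claim that power will rise, because they give no correlation between count and CPT. The Kaplan-Meier medians are not touched by the adjustment.

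**What to change.** In section 9.2:

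- Pre-specify one adjusted CPT comparison: the planned product model plus log(time-0 control-arm probing count + 1) for that session. Report it beside the unadjusted model. The + 1 deals with zero counts.
- State that the count is taken before the treated arm enters the cage and is assumed unaffected by the product on the other arm.
- State that later counts, or counts from a refreshed cage, will not be substituted.
- Decide separately whether to include a participant term, and reconcile section 9.2 with the synopsis, which names a different CPT model.

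The cost is a few sentences, one residual df (18 to 17) and no new data, with about 3 points of power lost if the count proves unrelated to CPT (about 8 if a participant term is added too). The covariate must be fixed before results are seen, since a choice made afterwards from 21 unblinded sessions would carry little weight. Balancing product order remains a separate need.
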